4.2.2 Pharmacokinetic Endpoints

PK endpoints (Cmax [µg/mL], Tmax [hr], AUC[0-T] [µg.hr/mL], Ctrough [µg/mL], AUC[TAU] [µg.hr/mL], AUC[INF] [µg.hr/mL], CL [L/day], T-HALF, Vz, and Cmin [µg/mL]) will be evaluated using non-compartmental analysis, where feasible. In addition, nivolumab end of infusion and trough (Cmin) concentrations will be calculated at specified visits for certain study parts.

Parameter	Definition
Cmax	Maximum observed plasma concentration
Tmax	Time of maximum observed plasma concentration
AUC(TAU)	Area under the concentration time curve in one dosing interval
Ceoinf	End of infusion concentration
Cmin	Trough observed concentration
T-HALFeff	Effective serum half-life
CL	Total body clearance

Table 4.2.2-1:PK Parameters, Naming Conventions and Definitions

4.2.3 Biomarker Endpoints

Due to limited numbers of tumor samples collected and limited amount of tumor tissue, PD-L1 IHC is the only biomarker analyzed and reported on for this study.

PD-L1 expression is defined as the percent of tumor cells demonstrating plasma membrane PD-L1 staining of any intensity. PD-L1 expression at baseline (+ or -) will be a key endpoint for assessing associations with efficacy, due to the need to better understand its utility as a potential marker of associations with response in the combination setting. It will be measured in all patients with available archival tumor sample, and in patients with paired pre- and on-treatment biopsies in the expansion cohorts.

4.2.4 Immunogenicity

Endpoints for the study are incidence rates of persistent positive ADA as well as neutralizing positive ADA from initiation of each drug treatment and up to and including the follow-up period of the last study drug dosing. Based on recommendation from BMS Immunogenicity Council, Harmonization of Clinical Immunogenicity Reporting by an Initiative of the Therapeutic Protein Immunogenicity Focus Group of the American Association Pharmaceutical Scientists, and the FDA Guidance for Industry Immunogenicity Assessment for Therapeutic Protein Products, the following definitions will be applied.

ADA Status of a Sample:

- Baseline ADA-Positive Sample: ADA is detected in the last sample before initiation of treatment
- ADA-Positive Sample: After initiation of treatment, (1) an ADA-positive sample in a subject who is baseline ADA-negative, or (2) an ADA-positive sample with ADA titer to be significantly increased (at least 9-fold for lirilumab and at least 4-fold for nivolumab) relative to baseline according to the corresponding analyte assay.
- ADA-Negative Sample: After initiation of treatment, ADA not-positive sample relative to baseline

ADA Status of a Subject:

- Baseline ADA-Positive Subject: A subject with baseline ADA-positive sample
- ADA-Positive Subject: A subject with at least one ADA-positive sample relative to baseline at any time after initiation of treatment during the defined observation time period, such as:
 - Persistent Positive: ADA-positive sample at 2 or more sequential timepoints, where there
 is an adequate elapse of time between the first and last ADA-positive samples (16 weeks
 for both BMS-986015 and nivolumab)
 - Only the Last Sample Positive: Not persistent but ADA-positive sample in the last sampling timepoint
 - Other Positive: Not persistent but some ADA-positive samples with the last sample being negative
 - Neutralizing Positive: At least one ADA-positive sample with neutralizing antibodies detected.

• ADA-Negative Subject: A subject with no ADA-positive sample after the initiation of treatment

5 SAMPLE SIZE AND POWER

5.1 Dose Escalation (Part 1; Completed)

As this is a Phase 1/2 dose escalation cohort, the sample size at each dose cannot be determined exactly, as it depends on the number of observed toxicities. Between 3 and 12 subjects approximately are expected to be treated during dose escalation in each Dose Level, and up to 15 subjects may be dosed at selected Dose Levels.

5.2 Cohort Expansion (Part 1; Completed)

During cohort expansion, approximately 18 subjects are expected to be enrolled in each of the 3 unknown or low historic response cohort expansions and 35 subjects in the 2 cohorts with higher historic ORR and treated at the previously determined MTD, MAD, or at an alternative dose that is not to exceed the MAD.

CRC, SCCHN, and HCC cohorts: The sample size for each tumor cohort will be guided by a 2-stage Gehan design.²¹ In order to determine whether a target ORR is likely in a tumor cohort, 9 subjects will be treated at Stage 1 in each tumor type, as outlined in Table 2.1.1.2-1. For a tumor type in which no responses are observed, it will be concluded that the true ORR is unlikely to be greater than or equal to the target ORR and no more subjects will be enrolled in these tumor cohorts. Otherwise, for the tumor cohort(s) in which at least 1 response among the first 9 subjects is observed, up to an additional 9 subjects will be enrolled as guided by Table 2.1.1.2-2. With 9 subjects in Stage 1, per tumor there is no more than a 10% chance of declaring that there is no therapeutic effect when actually there is an effect. A total of up to 18 subjects across the 2 stages per tumor will guarantee an estimate of the true ORR with 12% precision.

NSCLC and MEL cohorts: Thirty-five subjects will be enrolled in each of these tumor cohorts based on achieving a higher precision with a reasonable control on the type I error. In a cohort of 35 subjects, if 12, 14, or 16 responses are observed, then the lower limit of the 1-sided 90% CI for the ORR is 24%, 29%, or 34%, respectively. In addition, 19 responses would need to be observed in 35 subjects so that the 90% 1-sided CI for the ORR is entirely above 20%. These calculations are based on the lower limit of the Clopper-Pearson method for exact CIs. If the true ORR in a tumor type is 45%, then with 35 subjects in a cohort there is 96% chance of observing at least 10 responses, and 93% chance of observing at least 11 responses, and there is 7% chance of observing 10 or fewer responses (false negative rate). If the true ORR for a tumor is only 30% rather than 45%, then there is a 35% and 14% chance, respectively, that there will be at least 12 or at least 14 responses in 35 subjects (false positive rate).

The above numbers are approximate, as subjects treated during dose escalation with a tumor under the same setting (eg, dose and population) as in cohort expansion may be included in the total n per tumor.

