 - ◆ NSCLC and MEL Cohorts: A total of approximately 35 subjects will be enrolled per tumor cohort based on achieving a higher precision with a reasonable control on the type I error. In a cohort of approximately 35 subjects, if 12, 14, or 16 responses are observed, then the lower limit of the 1-sided 90% confidence interval (CI) for the ORR is 24%, 29%, or 34%, respectively. In addition, 19 responses would need to be observed in approximately 35 subjects so that the lower limit of the 1-sided 90% CI for the ORR is 42%. These calculations are based on the Clopper-Pearson method for exact CIs. If the true ORR in a tumor type is 45%, then with approximately 35 subjects in a cohort there is 96% chance of observing at least 10 responses, and 93% chance of observing at least 11 responses, and there is 7% chance of observing 10 or fewer responses (false negative rate). If the true ORR for a tumor is only 30% rather than 45%, then there is a 35% and 14% chance, respectively, that there will be at least 12 or at least 14 responses in approximately 35 subjects (false positive rate).
 - **The SCCHN Cohort Expansion (Part 2; Completed):** See [Section 1](#) “Clinical Experience with Lirilumab and Nivolumab Combination Treatment” of the protocol body for a summary of preliminary safety and efficacy results. A total of approximately 35 subjects will be enrolled in the SCCHN Expansion Cohort (Part 2; completed). The null hypothesis that the true ORR is 25% will be tested against a 1-sided alternative: ORR = 40%. The null hypothesis will be rejected if 12 or more responses are observed in 35 subjects. This design gives a 1-sided type 1 error rate of 0.15 and a power of 0.81.
 - **The SCCHN Randomized Cohorts (Part 3 - closed to enrollment):** The SCCHN Randomized Cohorts (Part 3) has a primary endpoint of ORR. Overall 2-sided alpha is set at 0.10. The final analysis of ORR will take place 6 months after last patient first treatment. A total of approximately 225 subjects will be enrolled if PD-L1 is expressed in $\geq 1\%$ of tumor cells, and will be randomized in a 2:1 ratio to the 2 treatment arms, nivolumab combined with lirilumab (Arm A) and nivolumab monotherapy (Arm B), stratified by PD-L1+ $\geq 50\%$ expression (yes/no) and prior treatment with cetuximab (yes/no). The sample size considers the

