8.1.2 Cohort Expansion (Part 1; Completed)

During cohort expansion, approximately 18 subjects are expected to be enrolled in each of the 3 unknown or low historic response cohort expansions and approximately 35 subjects in the 2 cohorts with higher historic ORR and treated at the previously determined MTD, MAD, or at an alternative dose that is not to exceed the MAD.

CRC, SCCHN, and HCC cohorts: The sample size for each tumor cohort will be guided by a 2-stage Gehan design.³⁸ In order to determine whether a target ORR is likely in a tumor cohort, 9 subjects will be treated at Stage 1 in each tumor type, as outlined in [Table 3.1.1.2-1](#). For a tumor

type in which no responses are observed, it will be concluded that the true ORR is unlikely to be greater than or equal to the target ORR and no more subjects will be enrolled in these tumor cohorts. Otherwise, for the tumor cohort(s) in which at least 1 response among the first 9 subjects is observed, up to an additional 9 subjects will be enrolled as guided by Table 3.1.1.2-2. With 9 subjects in Stage 1, per tumor there is no more than a 10% chance of declaring that there is no therapeutic effect when actually there is an effect. A total of up to 18 subjects across the 2 stages per tumor will guarantee an estimate of the true ORR with 12% precision.

NSCLC and MEL cohorts: A total of approximately 35 subjects will be enrolled in each of these tumor cohorts based on achieving a higher precision with a reasonable control on the type I error. In a cohort of approximately 35 subjects, if 12, 14, or 16 responses are observed, then the lower limit of the 1-sided 90% CI for the ORR is 24%, 29%, or 34%, respectively. In addition, 19 responses would need to be observed in approximately 35 subjects so that the 90% 1-sided CI for the ORR is entirely above 20%. These calculations are based on the lower limit of the Clopper-Pearson method for exact CIs. If the true ORR in a tumor type is 45%, then with approximately 35 subjects in a cohort there is 96% chance of observing at least 10 responses, and 93% chance of observing at least 11 responses, and there is 7% chance of observing 10 or fewer responses (false negative rate). If the true ORR for a tumor is only 30% rather than 45%, then there is a 35% and 14% chance, respectively, that there will be at least 12 or at least 14 responses in approximately 35 subjects (false positive rate).

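### NSCLC and melanoma cohorts (n = 35): 11 responses, not 19, put the 1-sided 90% limit above 20%, and the 96%, 93% and 7% at ORR 45% sit at cutoffs one response too low

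*SAP*

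**What the plan says.** The text concerns the NSCLC and melanoma expansion cohorts of Part 1. The SAP fixes the size: "Thirty-five subjects will be enrolled in each of these tumor cohorts" (the protocol says approximately 35). Protocol 8.1.2 and SAP 5.2 both name the Clopper-Pearson lower limit as the method.

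- **Lower limits.** SAP 5.2, taking counts of 12, 14 and 16 in turn: "then the lower limit of the 1-sided 90% CI for the ORR is 24%, 29%, or 34"%. The protocol gives the same three limits.
- **The 19-response sentence.** SAP 5.2: "19 responses would need to be observed in 35 subjects so that the 90% 1-sided CI for the ORR is entirely above 20"%. Protocol 8.1.2 gives the same count, "so that the 90% 1-sided CI for the ORR is entirely above 20"%. The protocol synopsis (Statistical Methods, Sample Size Determination) uses the same count but words the purpose as "so that the lower limit of the 1-sided 90% CI for the ORR is 42"%.
- **Probabilities at a true ORR of 45%.** SAP 5.2: "there is 96% chance of observing at least 10 responses, and 93% chance of observing at least 11 responses". For the complement of the second event, the SAP then adds that "there is 7% chance of observing 10 or fewer responses (false negative rate"). Protocol 8.1.2 and the synopsis print the same three figures.
- **Probabilities at a true ORR of 30%.** All three places give 35% for at least 12 responses and 14% for at least 14.

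**The concern.** The 19-response sentence conflicts with the sentence just before it. If 12 responses already give a lower limit of 24%, then 19 cannot be required to clear 20%. It also conflicts with the synopsis, which ties the same 19 of 35 to 42%.

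The probabilities at ORR 45% disagree with the exact binomial distribution at the stated n, although the ones at ORR 30% agree with it.

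This paragraph is the stated justification for 35 subjects per cohort. Anyone quoting it in a report would carry forward a response threshold that is too high by 8 (19 − 11) and a false-negative rate about twice the true one. They would also find the SAP at odds with the protocol synopsis.

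**Working it through.** **Inputs.** n = 35; 1-sided 90% Clopper-Pearson lower limit; true ORR 45% and 30% (all from SAP 5.2 and Protocol 8.1.2).

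**Formulas.** For r responses in n subjects, the lower limit L solves P(X ≥ r | n, L) = 0.10, so L is the 0.10 quantile of Beta(r, n − r + 1). The tail probabilities are exact Binomial(n, p) sums.

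**Step 1: reproduce the figures not in dispute (n = 35).**

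| Quantity | Computed | Printed |
|---|---|---|
| Lower limit, 12 responses | 23.54% | 24% |
| Lower limit, 14 responses | 28.67% | 29% |
| Lower limit, 16 responses | 33.95% | 34% |
| P(X ≥ 12), ORR 30% | 34.84% | 35% |
| P(X ≥ 14), ORR 30% | 13.50% | 14% |

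All five agree after rounding, so the method and n are as stated.

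**Step 2: the 19-response sentence.** Same formula, n = 35:

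| Responses | Lower limit |
|---|---|
| 10 | 18.57% |
| 11 | 21.03% |
| 18 | 39.37% |
| 19 | 42.13% |

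The smallest count with a limit above 20% is 11. Nineteen gives 42%, as in the synopsis, and is also the smallest count with a limit above 40%.

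Other interval methods do not rescue the sentence. The minimum count for a limit above 20% is 12 with a 2-sided 90% Clopper-Pearson interval (21.1%), 13 with a 2-sided 95% one (21.5%), 11 with a 1-sided Wald limit (21.4%) and 11 with a 1-sided Wilson limit (22.4%).

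A somewhat different n does not rescue it either. For every n from 30 to 36, 11 responses already give a limit above 20% (from 24.8% at n = 30 down to 20.4% at n = 36).

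**Step 3: probabilities at ORR 45%, n = 35.**

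| Event as printed | Printed | Exact | One cutoff higher | Exact |
|---|---|---|---|---|
| At least 10 | 96% | 98.48% | At least 11 | 96.46% |
| At least 11 | 93% | 96.46% | At least 12 | 92.71% |
| 10 or fewer | 7% | 3.54% | 11 or fewer | 7.29% |

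The printed values are the right-hand ones, rounded. The printed false-negative rate is about twice the exact one (7 / 3.54 ≈ 2).

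**Step 4: could another n explain the probabilities?** Computing the three printed events at ORR 45% for each n from 30 to 40, none gives 96/93/7. The closest are:

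- n = 32: 96.11 / 91.85 / 8.15%
- n = 33: 97.13 / 93.77 / 6.23%

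At n = 32 the ORR 30% figures would also change, to 22.8% and 6.9%, against the printed 35% and 14%.

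**The case against.** The arithmetic is not open to dispute; the objections concern weight, cause and remedy.

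- **Little depends on it.** The primary objective of Part 1 is safety and tolerability, its enrollment is complete, and the planned efficacy output in SAP 7.5 is ORR with a 2-sided 95% interval. Only the CRC, SCCHN and HCC cohorts have a response-based enrollment rule. This stands and limits the consequence. It does not make the printed figures right.
- **The reader can recover the truth.** The synopsis has 42%, and the 24% for 12 responses stands just before the faulty sentence. Nineteen responses do put the limit above 20%; they are simply not needed. That is so, but the sentence states a requirement, and the synopsis and body still disagree.
- **The numbers are declared approximate.** Protocol 8.1.2 and SAP 5.2 carry that caveat because matching dose-escalation subjects may be counted in n. It concerns n, and steps 2 and 4 show that n does not explain the gaps.
- **The cause of the shifted probabilities is inferred.** A true ORR of 42% at the printed cutoffs gives 96.503%, 92.7% and 7.3%, which nearly fits. The first value rounds to 97%, however, and all three places state 45%. A one-response slip is the better fit, but the documents do not show how it arose. The mismatch between the printed cutoffs and probabilities at 45% is certain either way.
- **The probability errors are conservative.** They understate the chance of seeing responses and overstate the false-negative rate. True, but the figures are still wrong as labelled.

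**Conclusion.** Both errors are confirmed.

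1. Protocol 8.1.2 and SAP 5.2 overstate the count needed for a limit above 20%: 19 printed, 11 by the stated method. The 19 belongs with 42%, as the synopsis has it.
2. The synopsis, Protocol 8.1.2 and SAP 5.2 all misstate three operating characteristics at ORR 45%. The differences are 2.5 points (96% printed, 98.5% exact), 3.5 points (93%, 96.5%) and 3.5 points (7%, 3.5%).

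The conclusion rests only on n = 35, the named exact method and the stated true ORR, and the undisputed figures in the same paragraph confirm all of these. The practical effect is on the record: an inconsistent and partly wrong sample-size justification for a completed part. The documents do not show whether the author of the 19-response sentence meant 42% or above 40%.

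**What to change.** - **Protocol 8.1.2 and SAP 5.2, 19-response sentence.** Align it with the synopsis: 19 of 35 responses give a lower limit of 42%. If a threshold statement was intended, say that the limit lies above 40%. Should 20% have been the intended threshold, the count to print is 11, and the synopsis would have to be matched to it.
- **Synopsis, Protocol 8.1.2 and SAP 5.2, probabilities at ORR 45%.** Either raise each cutoff by one (96% for at least 11, 93% for at least 12, 7% for 11 or fewer), or keep the cutoffs and print 98%, 96% and 4%. Keeping the cutoffs is correct whatever caused the mismatch.

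The cost is a text correction in three places. Sample size, decision rules and planned analyses stay as they are.

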5.3 The SCCHN Cohort Expansion (Part 2; Completed)

More than 35 subjects will be enrolled in the SCCHN Cohort Expansion (Part 2). The null hypothesis that the true ORR is 25% will be tested against a 1-sided alternative: ORR = 40%. The null hypothesis will be rejected if 12 or more responses are observed in 35 subjects. This design gives a 1-sided type 1 error rate of 0.15 and a power of 0.81.

5.4 The SCCHN Randomized Cohorts (Part 3)

The SCCHN Randomized Cohorts (Part 3) has a primary endpoint of ORR. A total of 225 subjects will be randomized in a 2:1 ratio to the 2 treatment arms, nivolumab combined with lirilumab (Arm A) and nivolumab monotherapy (Arm B), stratified by PD-L1 \geq 50% expression (yes/no) and prior treatment with cetuximab (yes/no).

Objective Response Rate:

The sample size is calculated to assess the ORR of lirilumab in combination with nivolumab. The type 1 error is set to 0.10 (2-sided) with no planned interim analysis. The final analysis for ORR will take place approximately 6 months after the last subject is randomized and treated. With 150 subjects in Arm A, if 50 responses are observed, the estimated ORR will be 33% and the 90% CI will be [26%, 41%]. In Study CA209041, the 90% CI for the nivolumab arm in PD-L1+ (> 1%) subjects was [9%, 25%].

The above sample size calculation was performed using EAST[®] 6 and SAS 9.2.

5.5 The Signal Detection Cohort Expansion (Part 4)

Removed with Revised Protocol 12.

5.7 The Signal Detection in Previously Untreated MEL with Lirilumab, Nivolumab, and Ipilimumab Combination (Part 6)

Removed with Revised Protocol 12.

6 STUDY PERIODS, TREATMENT REGIMENS AND POPULATIONS FOR ANALYSES

6.1 Study Periods

This study consists of 3 periods: pre-treatment, on-treatment, and post-treatment/follow-up period.

The pre-treatment period covers from the time of signing of the informed consent form to prior to the first dose of study medication.

The on-treatment period starts at the time of the first dose of study medication and extends to the time of decision to discontinue a subject from study therapy or when the subject completes therapy per protocol.

The post-treatment clinical follow-up period begins the day after the on-treatment period ends and extends to up to 150 days after the last dose of lirilumab or nivolumab or ipilimumab, as long as the patients are still enrolled in the study.

Additional follow-up for survival outcomes may extend to up to 3 years after initiation of study drug.

6.2 Treatment Regimens

The treatment group "as randomized/assigned" will be retrieved from the IRT system, if applicable. The treatment group "as treated" will be the same as the arm as randomized/assigned by IRT. However, if a participant received an incorrect treatment for the entire period of treatment, the participant's treatment group will be defined as the incorrect treatment the participant actually received.

6.3 Populations for Analyses

- All Enrolled Subjects: All subjects who signed an informed consent and were registered into IRT;
- All Treated Subjects: All subjects who have received at least one dose of study medication;
- Response-Evaluable Subjects: All treated participants with measurable disease at baseline and one of the following: 1) at least one post-baseline tumor assessment, 2) clinical progression, or 3) death
- All Randomized Subjects: all subjects who were randomized in Part 3. This population will be used for listing of randomization schedule for Part 3 only.
- Lirilumab PK: all subjects who receive at least 1 dose of lirilumab and have adequate serum concentration data for lirilumab PK.
- Nivolumab PK: all subjects who receive at least 1 dose of nivolumab and have adequate nivolumab PK.
- Lirilumab Immunogenicity: all subjects who receive at least 1 dose of lirilumab and have at least 1 ADA sample available.
- Nivolumab Immunogenicity: all subjects who receive at least 1 dose of nivolumab and have at least 1 ADA sample available.
- Biomarker: all treated subjects who have biomarker data available.

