5.7.3.3 Pharmacokinetics, Immunogenicity (Anti-drug antibodies) and Biomarker Assessment Schedules

Detailed schedules of the PK, immunogenicity (ADA), and biomarker assessments are presented below for all study parts. Effective with Revised Protocol 12, PK and ADA samples will continue to be collected but will not be analyzed except as clinically indicated in specific cases such as Grade 3/4 toxicity, infusion reactions, etc.

Table 5.7.3.3-1: PK, Immunogenicity (ADA) and Biomarker Assessment Schedule: Dose Escalation (the Dose Escalation and Cohort Expansion [Part 1; completed])

Study Week	Collection Timing				Serum				Tumor Archived Tumor Sample
	Study Day	Relative Study Day	Time (Event)	Time	PK anti-KIR	PK anti-PD-1	ADA anti-KIR	ADA anti-PD-1	
Screening									X
Week 1	C1D1	D1	0 h ^b	00:00	X	X	X	X	
	C1D1	Dj1	EOI ^c		X	X			
	C1D2	D2	24 h ^d	24:00	X				
	C1D8	D8	168 h ^d	168:00	X				
Week 3	C1D15	D15	336 h ^b	336:00	X	X	X	X	
Week 5	C1D29	D29	0 h ^b	00:00	X	X	X	X	
Week 13	C2D29	D85	0 h ^b	00:00	X	X	X	X	
	C2D29	D85	EOI ^c		X	X			
	C2D30	D86	24 h ^d	24:00	X				
	C2D36	D92	168 h ^d	168:00	X				
Week 17	C3D1	D113	0 h ^b	00:00	X	X	X	X	
Week 33	C5D1	D225	0 h ^b	00:00	X	X	X		
Week 49	C7D1	D337	0 h ^b	00:00	X	X	X		
Week 65	C9D1	D449	0 h ^b	00:00	X	X	X		

Table 5.7.3.3-1: PK, Immunogenicity (ADA) and Biomarker Assessment Schedule: Dose Escalation (the Dose Escalation and Cohort Expansion [Part 1; completed])

Collection Timing					Serum				Tumor
Study Week	Study Day	Relative Study Day	Time (Event)	Time	PK anti-KIR	PK anti-PD-1	ADA anti-KIR	ADA anti-PD-1	
Week 81	C11D1	D561	0 h ^b	00:00	X	X	X		
EOT					X	X	X	X	
Follow-ups 1-3					X	X	X		

^b Samples to be collected prior to the infusion of nivolumab.

^c Samples must be collected immediately following the end of lirilumab infusion. It is imperative that the actual time that the sample is obtained is recorded. All listed studies should be obtained prior to this point.

^d Samples may be collected at any time during the day, but it is imperative that the actual time that the sample is obtained is recorded.

C = Cycle; CBC = complete blood count; D = Day; EOI = End of Infusion; EOT = End of Treatment.

Table 5.7.3.3-2: PK, Immunogenicity (ADA) and Biomarker Assessment Schedule: Cohort Expansion (except for subjects with MEL or SCCHN) (the Dose Escalation and Cohort Expansion [Part 1; completed])

Collection Timing					Serum				Tumor

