7.6.5 Select Adverse Events

Summary of Select Adverse Events of Hypersensitivity/Infusion Reaction will be provided by ADA Status (Positive, Negative) for all Immunogenicity Subjects by treatment group and overall.

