7.8 Immunogenicity (ADA)

The analysis may include the following presentations; modifications may occur based on the evolving understanding of the regulatory or other BMS updates on standards for reporting ADA.

Summary tables will be generated for Part 1 and 2 combined. Listings will include all available data from Parts 1, 2, 3, and 5.

Summary:

- The number (%) of subjects with the following anti-drug responses will be reported by dose, if applicable, and overall, for each analyte:
- Baseline ADA-Positive
- ADA-Positive

- Persistent Positive
- Only the Last Sample Positive
- ADA-Positive with Neutralizing Positive
- ADA-Negative

Listing:

All collected immunogenicity will be listed with flags indicating baseline-positive sample, ADA-positive sample or ADA-negative sample.

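### The SAP's immunogenicity sets and ADA-negative definition count subjects with no post-baseline ADA result as negative

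*SAP*

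**What the plan says.** - **Entry to the sets.** SAP 6.3 takes "all subjects who receive at least 1 dose of lirilumab and have at least 1 ADA sample available" for lirilumab and "all subjects who receive at least 1 dose of nivolumab and have at least 1 ADA sample available" for nivolumab. Protocol 8.2 uses the same rule. Whether *available* means collected or assayed is not defined. In the same SAP list, the PK sets ask for adequate PK data and the biomarker set asks for data; only the immunogenicity sets are defined by a sample.
- **Subject status.** SAP 4.2.4 defines an ADA-negative subject as "A subject with no ADA-positive sample after the initiation of treatment". Protocol 8.3 agrees.
- **Sample status.** A negative sample is "After initiation of treatment, ADA not-positive sample relative to baseline". A positive sample needs either a baseline-negative subject or a titer rise over baseline (at least 9-fold for lirilumab, 4-fold for nivolumab).
- **Tables.** In SAP 7.8, "The number (%) of subjects with the following anti-drug responses will be reported by dose, if applicable, and overall, for each analyte". No denominator is named there. Summaries cover Parts 1 and 2 combined; Parts 3 and 5 are listed only. SAP 7.6.5 states: "Summary of Select Adverse Events of Hypersensitivity/Infusion Reaction will be provided by ADA Status (Positive, Negative) for all Immunogenicity Subjects".
- **Testing from Revised Protocol 12.** Protocol 5.7.3.3 and 5.9.1 keep collecting ADA samples, but these "will not be analyzed except as clinically indicated in specific cases such as Grade 3/4 toxicity, infusion reactions, etc".

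**The concern.** The negative label is defined by the absence of a positive, and entry to the denominator does not require that a positive could have been found. Untested and tested-negative subjects therefore share one category. This lowers the reported ADA incidence, which Protocol 8.3.2.1 names as a secondary endpoint for Parts 1 and 2. It also mixes subjects of unknown status into the comparison group of the table meant to show whether ADA goes with hypersensitivity or infusion reactions. Neither SAP 4.2.4, 7.6.5 nor 7.8 has a not-evaluable category to hold them.

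A smaller issue is the change in assay policy under Revised Protocol 12. Once assays are run only on clinical indication, late ADA status can depend on the safety events it is tabulated against.

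**Working it through.** The plan states no ADA rate, no expected share without a post-baseline result and no power for this endpoint, so there is no planned figure to reproduce. The check has three steps.

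**1. Apply the definitions literally.**

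| Subject | In set (6.3) | Status (4.2.4) | Column in 7.6.5 |
|---|---|---|---|
| Baseline negative, later sample positive | yes | positive | Positive |
| Baseline and later samples assayed, none positive | yes | negative | Negative |
| Pre-dose sample only | yes | negative, as no post-treatment positive exists | Negative |
| No baseline result, later sample positive in the assay | yes | neither positive-sample clause is met, so negative | Negative |

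The third row follows from the text alone. In the fourth row the first clause needs a baseline-negative subject and the second needs a baseline titer. A programmer could treat a missing baseline as negative and reach the opposite label; the SAP does not settle it.

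**2. Size of the dilution.** Let N be the set, d the share with no post-baseline result, and r the ADA-positive rate among the rest.

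- Positives = r(1 − d)N, so the reported rate = r(1 − d).
- Assumed r = 10%, d = 5%: 10% × 0.95 = 9.5%.
- Assumed r = 10%, d = 10%: 10% × 0.90 = 9.0%.
- Per 100 subjects at d = 10%: 90 have a result, 9 are positive and 81 are tested negatives. The Negative group is 81 + 10 = 91, of whom 10 (10/91 = 11%) have no post-baseline result.

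**3. Reach of the Revised Protocol 12 rule in Parts 1 and 2.** The rule dates from 08-May-2018. Protocol 8.3.2.1 schedules ADA at Weeks 1, 3, 5, 13, 17, 33, 49, 65 and 81, end of treatment and three follow-up visits. Week w falls 7(w − 1) days after first dose.

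- First dose on 12-Dec-2016 (Amendment 13, which describes enrollment in Parts 1 and 2 as complete): 512 days, or 73.1 weeks, before the rule. Week 65 is day 448 and falls before it; Week 81 is day 560 and falls after it.
- First dose on 13-Jul-2017: 299 days, or 42.7 weeks. Week 33 is day 224 and falls before the rule; Week 49 is day 336 and falls after it. This later date is an assumption, taken from the data cut-off in Protocol Section 1. It allows for the statement in Protocol 1.1.1 that Part 2 closes as Part 3 opens. The documents give no last-subject date.

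In both cases Weeks 1 to 33 precede the rule. Only later on-treatment samples, end of treatment and follow-up can be affected, in subjects still on study. This assumes that earlier samples had been assayed by then, which the documents do not say.

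The late samples still matter for one category. SAP 4.2.4 requires 16 weeks between first and last positive samples for persistent positivity. A subject first positive at Week 33 cannot qualify before Week 49 (49 − 33 = 16).

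**The case against.** The strongest reply is that these are narrow wording gaps in descriptive tables. The schedule includes post-baseline samples at Weeks 3, 5, 13 and 17 and at end of treatment, so a baseline-only subject must have missed all of them, and d is probably small. No test or dose decision depends on the result, and SAP 7.8 allows its presentations to be modified. This limits the size. It does not make an untested subject negative.

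Two stronger readings are tempting, and the documents do not support either.

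- *Unanalysed samples count as negative by rule.* A reader might infer this from *available*. The term is undefined, and SAP 4.2.4 assigns sample status by assay finding, so an unassayed sample has no status. This is an ambiguity to close.
- *After Revised Protocol 12 only subjects with toxicity are tested, so the infusion-reaction table is biased towards an association.* The Protocol's condition is clinical indication, and its examples are not exhaustive. The table covers Parts 1 and 2 only. Protocol 1.4.13.3 and 1.4.17.2 say infusion reactions came mainly with the first infusion, which on the dates above preceded the rule. Nothing says that an early reaction triggers assay of a sample drawn much later. The direction is also open: a subject who reacts at the first infusion and leaves with only a pre-dose sample is labelled negative, which works against an association. I therefore put no figure on this bias.

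The remedy can also be challenged. Requiring a baseline drops the missing-baseline positives, and setting aside for-cause results could leave a known positive tabulated as negative. Both objections stand, and the fix deals with them by listing and footnoting.

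**Conclusion.** The definitions are wrong as written: a subject with only a pre-dose sample is reported as ADA-negative, and a later positive without a baseline result has no correct place. Confidence in this is high because it rests on the text alone. The size is a factor of (1 − d) on the reported incidence. The 9.5% and 9.0% figures assume a 10% evaluable rate, with d of 5% and 10%; they show scale and do not estimate what this trial will report.

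The effect of restricted testing is secondary. In the summarised parts it is confined to late samples, chiefly affecting late positives and persistent-positive status, and it rests on the assumed first-dose dates.

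**What to change.** 1. In SAP 6.3, define ADA-evaluable subjects for each analyte as treated subjects with a baseline ADA result and at least one post-baseline ADA result, both assayed and not merely collected.
2. Name this set as the denominator in SAP 7.8 and 7.6.5. Report the remaining treated subjects as not evaluable, and list any subject with no baseline result and a later positive.
3. Flag each result assayed for cause under the Revised Protocol 12 rule. Base the 7.8 and 7.6.5 summaries on routinely scheduled assays, list for-cause results separately, and footnote any subject positive only on a for-cause assay.

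The cost is a revised population definition, a not-evaluable row and a sample flag, with no change to study conduct. The downside is a slightly smaller denominator and a slightly higher reported incidence.
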